H1. Compared with usual management, self-management of urinary symptoms with probiotics will reduce the frequency, severity and impact of urinary symptoms and UTIs (PRIMARY OUTCOMES). The goal of aim 2 is to assess the effect of *Lactobacillus* supplementation on the frequency, severity and impact of urinary symptoms and UTIs. This aim can be evaluated with all 100 participants in the SMP pilot study. We expect to find a significant difference in these primary outcomes between our three experimental timeframes (6 months prior to intervention, 6 months of SMP_{PRO} intervention, and 6 month follow-up period). Frequency of UTI will be defined as the number of verified UTIs occurring during the timeframe. Urinary symptoms will be assessed using the USQ-NB where frequency of symptoms, degree of severity, and impact on the individual, will be considered.

We will estimate the average number of symptoms on the USQ-NB endorsed (irrespective of frequency, severity and impact) across the weeks during that time frame, for each participant. Thus, each participant will have a continuous outcome (average number of USQ-NB items endorsed). We will also compute the number of verified UTIs experienced by each participant. These two outcomes are the primary outcomes for our study and analysis; they depend solely on the face validity of the USQ-NB, and on clinically verified UTIs, and so will not be affected by a failure to find or establish formal measurement properties for the USQ-NB, should any occur. They will also be less subject to any variability in participant perceptions of frequency, severity or impact, which can complicate analytic assumptions and limit power and interpretability of change that might be perceived. We will describe these features of the sample over time but will not conduct inference tests on these ratings.

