We propose linear mixed-effects modeling to explore the effect of introduction to/use of the SMP_{PRO} on the number of USQ-NB symptoms (averaged over the entire time frame) and the incidence of UTIs. Each model will include gender as a fixed effect, and time (baseline; SMP_{PRO} use; post-SMP_{PRO} observation) as the explanatory variable, and random effects for intercept (subject) only. This method allows for missing data and the inclusion of covariates where appropriate; however we plan post-hoc analyses of the modeling in order to pinpoint potential interaction effects (e.g., between age or sex and time). The focus of the analyses is to determine whether (irrespective of individual starting values or specific slopes) mean USQ-NB item endorsement and UTI counts go down in the SMP_{PRO} time frame relative to the baseline values (generally negative associations in each regression between the outcome and time) and whether these values stay flat (zero slope), continue to decrease (negative slope) or increase (positive slope) during the post-SMP_{PRO} follow up.

Power calculation: We plan to use mixed effects regression modeling for the most precision in our estimated effects of the SMP_{PRO} on the USQ-NB symptom rate and UTI rate. However, it is difficult to predict the exact form of the final models since our understanding of the USQ-NB symptom makeup, and the univariate associations between gender or age (or any other of the demographic variables we will collect) and these two outcomes. Therefore, for the most conservative estimates, we use the most basic analytic method to estimate the worst-case scenario power calculation, a t-test. In this pair of primary outcomes, alpha is set at 0.025 for each power calculation (and for each inference test). We will have data from 100 participants; however, to protect against a possible 20% drop out rate over the course of the 18-month study, we will recruit 120 persons for this arm, hoping for a final N of 100. If we observe an average of 25 items on the USQ-NB endorsed over the baseline period, then with alpha = 0.025 we would have 81% power to detect a reduction in this average number of items endorsed as low as five

The Impact of Self-Management with Probiotics on Urinary Symptoms and the Urine Microbiome in Individuals with Spinal Cord Injury and Spina Bifida Protocol
5/18/2017

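### The random-intercept-only model assumes equal variances and one common correlation across the three timeframes, with no safeguard, so contrast standard errors can be wrong in either direction

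*Combined protocol and SAP*

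**What the plan says.** Under H1 the plan expects the primary outcomes to differ "between our three experimental timeframes (6 months prior to intervention, 6 months of SMP_{PRO} intervention, and 6 month follow-up period"). Weekly questionnaires are averaged within each timeframe, so that "each participant will have a continuous outcome (average number of USQ-NB items endorsed"). Verified UTIs are counted per timeframe. Each person therefore contributes three values per outcome.

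The model has gender and time (three levels) as fixed effects and "random effects for intercept (subject) only". It is to show whether the outcomes "go down in the SMP_{PRO} time frame relative to the baseline values", and then "whether these values stay flat (zero slope), continue to decrease (negative slope) or increase (positive slope") in the follow-up period.

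The power paragraph states that "alpha is set at 0.025 for each power calculation (and for each inference test"). It bases power on a simpler test: "we use the most basic analytic method to estimate the worst-case scenario power calculation, a t-test".

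H2 (urinary white cells) and H3 (antibiotic use) also plan mixed models over time and explicitly compare the post-intervention period with baseline. H4 uses a mixed linear model for the Shannon Index.

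The plan says the final model form is hard to predict and allows Poisson modelling of UTI and antibiotic counts. No residual covariance structure, robust variance, sphericity check or fallback covariance is written for any of these models.

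**The concern.** A random intercept with independent residuals gives every period the same variance and every pair of periods the same correlation. Baseline and follow-up, whose midpoints are 12 months apart, are treated as being as alike as neighbouring periods. All three pairwise contrasts then share one pooled standard error, whatever the data show.

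The plan's own content gives reasons to doubt this:

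- Repeated measures often correlate less as they lie further apart.
- Instillation is triggered by symptoms, and a second one is the participant's choice. Exposure will therefore vary between people in the middle period only.
- H4 expects responders and non-responders, which would change the variance of differences that involve the treated period.
- If UTI variance is proportional to the mean, the planned fall from 6 to 4.75 lowers the variance by 1 - 4.75/6 = 21%.

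At stake is the validity of the primary p-values at alpha 0.025. Some contrasts could lose power and others could be declared significant too often.

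**Working it through.** **Inputs from the documents.** Final N 100; alpha 0.025 per primary outcome (sidedness not stated); a 5-item reduction with SD 16; a 1.25 UTI reduction with SD 4; stated power 81%; three periods.

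**Inputs assumed.** Between-period correlations and per-period SDs, because the documents give none.

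**Step 1: reproduce the plan's figure.** Use a one-sample (paired) test, two-sided alpha 0.025, z = 2.241.

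- USQ-NB: SE = 16/√100 = 1.6; 5/1.6 = 3.125; power = Φ(3.125 - 2.241) = 0.812.
- UTI: SE = 4/√100 = 0.4; 1.25/0.4 = 3.125; power again 0.812.
- The noncentral t gives 0.801.

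The plan's statement that "we would have 81% power to detect a reduction in this average number of items endorsed as low as five" is therefore reproduced. A two-sample test with 100 per group gives 0.487, which does not match. If SD 16 is a per-period SD, as worded, an SE of 1.6 requires 2 × 256 × (1 - r) = 256, so r = 0.5 is assumed silently. The calculation covers only the change from baseline to the intervention period and does not address the three-period covariance.

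**Step 2: standard errors under the two models, complete data.** Let V_ij = s_i² + s_j² - 2·r_ij·s_i·s_j be the variance of a between-period difference.

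- Correct SE of a contrast (and the unstructured one): √(V_ij/N).
- Random-intercept SE of every contrast: √(mean of the three V / N).
- With equal SDs the ratio (random intercept to correct) is √((1 - mean r)/(1 - r_ij)).
- Type I error ≈ 2·P(T with 99 df > 2.259 × ratio), where 2.259 is the critical value on 198 df.

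Example, correlations 0.7 (baseline-SMP), 0.7 (SMP-follow-up), 0.5 (baseline-follow-up): mean r = 0.633. The adjacent ratio is √(0.367/0.3) = 1.106. The baseline-follow-up ratio is √(0.367/0.5) = 0.856.

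| Assumed correlations, same order (SD 16 unless stated) | Baseline-SMP | SMP-follow-up | Baseline-follow-up |
|---|---|---|---|
| 0.5/0.5/0.5 (compound symmetry) | 1.00 (0.026) | 1.00 (0.026) | 1.00 (0.026) |
| 0.6/0.6/0.5 (mild decay) | 1.04 (0.021) | 1.04 (0.021) | 0.93 (0.038) |
| 0.6/0.6/0.36 | 1.10 (0.015) | 1.10 (0.015) | 0.87 (0.053) |
| 0.7/0.7/0.5 | 1.11 (0.014) | 1.11 (0.014) | 0.86 (0.056) |
| 0.8/0.8/0.65 | 1.12 (0.013) | 1.12 (0.013) | 0.85 (0.059) |
| 0.4/0.4/0.7 (treated period differs) | 0.91 (0.042) | 0.91 (0.042) | 1.29 (0.004) |
| 0.5/0.5/0.5, SDs 16, 12, 12 | 0.95 (0.035) | 1.14 (0.012) | 0.95 (0.035) |
| 0.5/0.6/0.4, SDs 16, 12, 14 | 1.00 (0.027) | 1.22 (0.007) | 0.87 (0.052) |

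Entries are the SE ratio, with type I error at nominal 0.025 in brackets.

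Power for the 5-item change at 0.6/0.6/0.36 is about 0.85 with the random intercept and 0.89 with an unstructured matrix.

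**Step 3: can an unstructured matrix be fitted?** It has 3 variances and 3 correlations, so 6 parameters. Simulation used 1,000 trials for each of four patterns, with 120 enrolled and 20% monotone dropout (120 × 0.8 = 96 completers on average). The unstructured model converged in every trial, with type I error 0.015-0.032 (Monte Carlo SE about 0.005). The random-intercept model showed the same pattern as the table: 0.044 for baseline-follow-up at 0.6/0.6/0.36, and 0.044 for baseline-SMP at 0.4/0.4/0.7.

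**The case against.** A reader might infer that the planned standard errors are wrong in known directions: too large for the powered contrast and too small for follow-up versus baseline. The documents do not support that. They give no between-period correlations or per-period variances, and under compound symmetry there is no error. That pattern of directions belongs to decaying correlation. If treatment makes the middle period unlike two similar off-treatment periods, the powered contrast becomes the anti-conservative one. With SDs 16, 12, 14 and correlations 0.5/0.6/0.4 it is essentially unaffected. This objection stands, and it limits the claim to a risk of unknown direction.

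Three further points have weight:

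- Each outcome value summarises a six-month period in people with a chronic condition, so mild decay and small errors are plausible.
- The contrasts spelled out in the H1 model paragraph are both between adjacent periods, and under decay both are conservative. Follow-up versus baseline falls within H1's three-timeframe comparison but is explicit only for the secondary hypotheses H2 and H3.
- The text describes only random effects, so equal correlation also rests on the usual independent residuals. This is a gap in specification and not a demonstrated error.

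The remark that the final model form is hard to predict does not fill the gap. It concerns symptom makeup and covariate associations, and the Poisson option addresses non-normality.

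The estimability argument at N of about 100 also does not extend to the urine subsample. Its size is given as 30 under Phase III, 20 under H2 and 50 under H4, with up to 18 samples per person. An unstructured 18 × 18 matrix would need 18 × 19/2 = 171 parameters.

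**Conclusion.** The point holds as a conditional one. The written model makes an assumption about variances and correlations that the plan neither justifies, checks nor protects against. Contrast standard errors can be wrong in either direction unless the variances of the period differences are equal.

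The size rests wholly on assumed correlations, with complete data at N = 100 and two-sided alpha 0.025. It runs from nothing under compound symmetry, through 4% and 7% under mild decay, to 10-12% too large (adjacent periods) and 13-15% too small (follow-up versus baseline) under stronger decay. Under the treated-period-differs pattern the main contrast has type I error of about 0.042 instead of 0.025.

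This does not show that the planned analysis will mislead. It is a low-cost improvement worth making, because the sponsor cannot know beforehand that any error would fall on the safe side.

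**What to change.** - **Three-timeframe linear models of the primary outcomes:** specify an unstructured 3x3 within-subject covariance with small-sample degrees of freedom (for example Kenward-Roger), or keep the random intercept and use robust (sandwich) standard errors.
- **UTI or antibiotic counts, if modelled as Poisson:** use GEE or robust standard errors, because an unstructured residual matrix does not carry over directly.
- **White-cell and Shannon models in the urine subsample:** keep the random intercept and use small-sample-corrected robust standard errors, not an unstructured matrix.

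The cost is a sentence or two in the SAP, a few more covariance parameters and slightly fewer degrees of freedom. If compound symmetry holds, essentially nothing is lost: with SD 16 and correlation 0.5 the standard error is 1.600 under both models.

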(i.e., to detect a change from an average of 25 to an average of 20) during the SMP_{PRO} period, assuming that the standard deviation of the average number of endorsed USQ-NB items is as high as 16. If we observe an average of one UTI per month in the initial 6-month period (for an average of six UTIs across this sample of 100 persons), then, with the alpha of 0.025 we would have 81% power to detect a reduction in this average number of UTIs as low as 1.25 (i.e., to detect a change from an average of 6 to an average of 4.75) during the SMP_{PRO} period, assuming that the standard deviation of the number of UTIs is as high as 4. We will explore the consistency of the UTI variable with the assumption of a normal distribution, and if appropriate we may utilize Poisson modeling if the assumption of normality is violated.

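### Recruiting 120 with 20% dropout leaves 96 completers, not 100, and the 81% power is not shown to be a worst case

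*Combined protocol and SAP*

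**What the plan says.** In the combined protocol and SAP, the power paragraph under H1 gives the dropout allowance: "to protect against a possible 20% drop out rate over the course of the 18-month study, we will recruit 120 persons for this arm". The sample is then treated as 100. The paragraph states "We will have data from 100 participants" and, less firmly, "hoping for a final N of 100". The opening of H1 and the sentence on UTI power also use 100.

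On method, the plan says that "for the most conservative estimates, we use the most basic analytic method to estimate the worst-case scenario power calculation, a t-test". The significance level is fixed by "alpha is set at 0.025 for each power calculation (and for each inference test". For symptoms, the 81% power refers to a fall of five items, put as "to detect a change from an average of 25 to an average of 20) during the SMP_{PRO} period". The spread behind that claim is described separately, in these terms: "assuming that the standard deviation of the average number of endorsed USQ-NB items is as high as 16". For UTIs, the same 81% is claimed for a fall from 6 to 4.75 with an SD of up to 4, described as the SD of the UTI count.

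The power paragraph does not say whether the t-test is paired, whether it is one- or two-sided, or what within-person correlation is assumed. The Phase II design section gives 120 as an upper limit on enrolment and has participants act as their own controls over three consecutive six-month periods.

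**The concern.** Two things do not follow from the plan's own figures.

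First, the recruitment number, the dropout rate and the final sample stand together and do not agree. It looks as if 100 was multiplied by 1.2 instead of divided by 0.8. The power statement for both primary outcomes rests on the resulting 100.

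Second, the reader is told that the power is a worst case. That is a claim about a lower bound. In a before-and-after comparison, power depends on the SD of the within-person change. The SDs given are worded as SDs of the outcome itself, and turning one into the other needs a correlation that the plan does not state. If that correlation is lower than the calculation implies, power is below 81% and the label misleads.

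**Working it through.** **Inputs, all from the H1 power paragraph.** Recruited 120; dropout 20% over 18 months; analysed N = 100; alpha 0.025 per outcome; differences 5 items and 1.25 UTIs; SDs 16 and 4. Both outcomes have the same standardised difference, 5/16 = 1.25/4 = 0.3125, so one calculation serves for both.

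**Step 1: reproduce the 81%.** Take a two-sided paired test with 16 and 4 as SDs of change. The normal approximation is Φ(0.3125·√n − z), with z = 2.2414 for two-sided alpha 0.025.
- N = 100: Φ(3.125 − 2.2414) = 81.2%; noncentral t gives 80.1%.

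The plan's figure is recovered. A one-sided paired test with SDs of change gives 87.8% (normal) or 87.2% (noncentral t), which does not match.

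**Step 2: dropout.**
- Completers from 120: 120 × 0.80 = 96.
- Recruitment needed for 100 completers: 100/0.80 = 125.
- Loss that 120 can absorb and still leave 100: 20/120 = 16.7%.

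**Step 3: effect on power, same reading as Step 1.** The month-12 rows assume that loss is spread evenly over the 18 months; the plan gives no timing. Linear loss leaves 120 × (1 − 0.20 × 12/18) = 104; a constant hazard leaves 120 × 0.80^(12/18) = 103.4.

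| N | Basis | Normal | Noncentral t |
|---|---|---|---|
| 100 | as stated in the plan | 81.2% | 80.1% |
| 96 | completers at month 18 | 79.4% | 78.2% |
| 103 | month 12, even loss | 82.4% | 81.4% |
| 104 | month 12, even loss | 82.8% | 81.8% |

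**Step 4: the SDs as worded.** If 16 and 4 are SDs of the outcome in each period, taken as equal in both periods, the SD of change is SD × √(2(1 − ρ)), where ρ is the within-person correlation. It equals the stated SD only when ρ = 0.5. Solving for 81% at N = 100, two-sided, gives ρ = 0.498 (normal) or 0.511 (noncentral t). The documents give no value of ρ; the range below is assumed for illustration.

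| ρ | Two-sided power, N = 100, noncentral t |
|---|---|
| 0.3 | 64% |
| 0.4 | 72% |
| 0.5 | 80% |
| 0.6 | 89% |
| 0.7 | 96% |

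On this reading 81% sits inside the range and not at its lower end.

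**The case against.** The strongest reply is that the shortfall has almost no consequence. The contrast that was powered, baseline versus the SMP_PRO period, ends at month 12, whereas the 20% loss runs to month 18. The plan also says of its mixed model that "This method allows for missing data and the inclusion of covariates where appropriate", so people who leave later still contribute. With even loss, 103 to 104 people remain at month 12 and 81% holds. This stands, and it is why the severity is low. It does not make 100 the right number of completers, and H1 also asks what happens during follow-up to month 18, where 96 is the relevant figure.

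A second reply is that the 81% can be reproduced and that the design points to pairing: participants are their own controls and the model has a subject random intercept. That also stands. Pairing, however, does not settle which SD was meant.

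A third reply is that the worst-case wording refers to using a t-test in place of the mixed model, and that the SDs are given as upper values. This is a fair reading of the intent. Neither element bounds the correlation if the SDs are per-period.

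A reader might go further and infer that true power is near 48%, the two-sided result of an unpaired t-test with 100 values per period. The documents do not support that: it treats the same people as independent samples, against the own-control design. A correlation of zero likewise conflicts with the planned random intercept. Nor do the documents show that 81% is wrong or that the pilot must enrol more; power may be higher or lower than stated.

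**Conclusion.** The point holds at low severity. The final N of 100 is wrong as written: the plan's own rate gives 96 at month 18, and at most 96, since enrolment is capped at 120. The cost is about 2 points of power at month 18 (81.2% to 79.4%, or 80.1% to 78.2%), and possibly nothing for the month-12 contrast. These figures rest on a two-sided paired test with SDs of change, which is inferred because it reproduces 81%. The month-12 figures rest also on even loss.

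The worst-case and conservative labels are unsupported as applied to the 81%. With the SDs as worded, the figure depends on a correlation of about 0.5 that the plan never states.

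**What to change.** Wording only; no added enrolment.

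- In the H1 power paragraph, replace both statements of 100 with an expected 96 completers at month 18 from 120 enrolled. In the opening of H1 and in the UTI power sentence, change 100 to 96, or refer to up to 120 enrolled, whichever fits the sentence.
- Restate power for both outcomes as about 79% at 96 (normal approximation; 78% by noncentral t), labelled as a completers-only figure, and note that more participants may contribute to the month-12 contrast. If the test was in fact one-sided with SDs of change, the figure at 96 is about 86%. Name the test and its sidedness alongside.
- State that 16 and 4 are SDs of within-person change. If they are per-period SDs, report power over a range of correlations instead of one figure.
- Limit the worst-case and conservative wording to the choice of a t-test over the mixed model, or delete it.

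The cost is a stated power about 2 points less favourable or, if the SDs are per-period, a range that includes values well below 81%. Enrolment, endpoints and analysis do not change.

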H2. Compared with usual management, self-management of urinary symptoms with probiotics will reduce bladder inflammation (Secondary outcome). For those 20 participants in the subsample giving urine samples, bladder inflammation will be measured from each urine sample using a standard white blood count (WBC) from the urinalysis. WBC counts will be obtained only at the start of each timeframe, and so can be analyzed longitudinally as continuous variables representing the 6-month pre-treatment period and the 6 month-SMP_{PRO} period. As such we plan a mixed effects linear regression model of WBC counts with time treated as the factor of interest. This analysis will assess whether WBC is significantly different from the SMP_{PRO}, and post-SMP_{PRO}, relative to the baseline pre-treatment periods.

H3. Compared with usual management, self-management of urinary symptoms with probiotics will reduce the need for antibiotics to treat UTI (Secondary outcome). The number of times antibiotics are used for each patient will be obtained from their medical records or self report. This value will be analyzed with the same three-point longitudinal mixed effects regression model with time as the factor of interest. Depending on the distribution of the outcome (i.e. given the count nature of this outcome, it may be Poisson distributed), we will utilize either linear or Poisson regression models. This analysis will assess whether there is an association between UTI rate during use of the SMP_{PRO}, and post-SMP_{PRO} exposure, relative to UTI rate during the baseline pre-treatment period.

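### The only count-model fallback for the UTI co-primary is Poisson with no allowance for over-dispersion, so if used it could run at about 5% error instead of 2.5%, depending on a within-person variance the plan does not state

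*Combined protocol and SAP*

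**What the plan says.** Under H1, the number of verified UTIs per six-month timeframe is one of two primary outcomes. It is to be analysed by a linear mixed model with gender, time and a random intercept for subject only.

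The power paragraph states that "alpha is set at 0.025 for each power calculation (and for each inference test"). Its basis is given as "we use the most basic analytic method to estimate the worst-case scenario power calculation, a t-test". For UTIs the planning mean is stated as "for an average of six UTIs across this sample of 100 persons", and the plan claims that "we would have 81% power to detect a reduction in this average number of UTIs as low as 1.25", "assuming that the standard deviation of the number of UTIs is as high as 4".

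The paragraph closes with the fallback: the fit of the UTI variable to a normal distribution will be explored, and "if appropriate we may utilize Poisson modeling if the assumption of normality is violated". H3 (number of antibiotic courses) offers the same pair of models: "we will utilize either linear or Poisson regression models".

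Neither H1 nor H3 mentions a negative binomial model, a scale parameter, a robust variance or a check for over-dispersion. The correlation between a person's counts in different timeframes is not given.

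**The concern.** A Poisson model fixes the variance at the mean. A subject intercept relaxes this for stable differences between people, but not for extra variation within a person from one timeframe to the next. Such variation is plausible for recurrent infections. If it is present, the Poisson standard error of the time contrast is too small and the test is not held at 0.025. In a design where each person is his or her own control, that contrast carries all the evidence for effect.

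The trigger is also aimed at the wrong assumption. Counts are discrete and usually skewed, so a normality check is likely to fail. Yet non-normality does little harm to a mean contrast with about 100 people, and it says nothing on whether the variance equals the mean. The rule could therefore replace a test that holds its level with one that does not.

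**Working it through.** **Inputs.** From the H1 power paragraph: mean 6, reduction 1.25, SD 4, 100 people analysed, alpha 0.025 (sidedness not stated). From the H1 modelling paragraph: subject intercept only, assumed here to carry over to the Poisson fallback. The within-person correlation ρ is not in the documents. It is an assumption, varied below.

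**1. The plan's 81%.** Take 4 as the SD of the within-person change, with a two-sided test. The standard error is 4/√100 = 0.4, and 1.25/0.4 = 3.125. The critical value is 2.241, so power is Φ(3.125 − 2.241) = 81.2%. The noncentral t gives 80.1%. Other readings are further off:
- paired, one-sided: 87.2%
- two-sample, 100 per timeframe: 48.2% two-sided, 59.4% one-sided
- paired, two-sided: 78.2% with 96 people, 87.4% with 120

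**2. What Poisson allows.** With two complete timeframes, a Poisson model with a subject intercept tests the time effect through the split of each person's total. Gender is constant within person and drops out. Under no effect, the model takes Var(Y1 − Y2) = 6 + 6 = 12. If the true variance is V, then φ = V/12, the standard error is too small by a factor √φ, and the two-sided error is 2 × [1 − Φ(2.241/√φ)].

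**3. SD 4 read as the SD of the change.** V = 16, φ = 16/12 = 1.333 and √φ = 1.155. The error is 2 × [1 − Φ(2.241/1.155)] = 5.2%, about 2.1 times nominal. One-sided it would be 4.5%. For a 2-df test across all three timeframes with the same φ it would be 6.3%.

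**4. SD 4 read as the SD in each timeframe.** V = 2 × 16 × (1 − ρ) = 32(1 − ρ). The simulated columns use 20,000 trials per row, 100 people, two timeframes, gamma-mixed Poisson counts with mean 6 and variance 16, and no effect. All error rates are in percent, against a nominal 2.5.

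| ρ | SD of change | φ | Poisson, formula | Poisson, simulated | Paired t, simulated | Robust SE, simulated |
|---|---|---|---|---|---|---|
| 0 | 5.66 | 2.667 | 17.0 | 17.1 | 2.4 | 2.5 |
| 0.25 | 4.90 | 2.000 | 11.3 | 11.3 | 2.5 | 2.6 |
| 0.3 | 4.73 | 1.867 | 10.1 | – | – | – |
| 0.4 | 4.38 | 1.600 | 7.6 | 7.8 | 2.7 | 2.8 |
| 0.5 | 4.00 | 1.333 | 5.2 | 5.3 | 2.4 | 2.6 |
| 0.6 | 3.58 | 1.067 | 3.0 | 3.0 | 2.5 | 2.7 |
| 0.625 | 3.46 | 1.000 | 2.5 | 2.3 | 2.4 | 2.4 |
| 0.7 | 3.10 | 0.800 | 1.2 | – | – | – |

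The robust column is the log ratio of period totals with a person-clustered standard error.

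**5. Sensitivity to the ceiling.** By the formula in step 2, an SD of change of 3.75 gives 3.8% error, 3.5 gives 2.65%, and 3.25 gives 1.7%.

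**6. Power.** With counts falling from 6 to 4.75 and ρ set at 0.5 (simulated SD of change 3.8), power is about 86% with the robust standard error and 85% with the paired t test. Plain Poisson shows 92%, which is overstated because that test is liberal.

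**The case against.** A reader might infer that a mean of 6 with an SD of 4 (variance 16, or 16/6 = 2.67 times the mean) already proves Poisson invalid and the error doubled. The documents do not support that. A Poisson model with a subject intercept produces a marginal variance above the mean by construction. Between-person variance of 16 − 6 = 10 gives exactly these figures, at a correlation of 10/16 = 0.625, with no inflation.

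Nor do the documents establish that the excess is within person. Their words describe the SD of the count, not of the change. The change reading is inferred because it comes closest to 81%, and it gives 81.2% only by the normal approximation. The two co-primaries also share one standardised effect (5/16 = 1.25/4 = 0.3125), which suggests SDs chosen to fit a target effect size rather than taken from UTI data. The SD is stated as an upper value, and step 5 shows how quickly the inflation shrinks below it.

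Poisson is optional. The linear mixed model remains the stated analysis, and the wording leaves room to reject a Poisson model that fits badly. The study is also a pilot. For H3 there is no mean, SD or correlation, so inflation cannot be shown there.

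All of this stands, and it limits the claim to a possible inflation. It does not supply the missing safeguard: the plan gives no correlation, names no variance check, and ties the switch to normality instead.

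**Conclusion.** The point holds as a conditional one and should be fixed, with moderate confidence. If Poisson is used and 4 is the SD of the within-person change, the two-sided error is about 5% instead of 2.5%. If 4 is the SD in each timeframe, the error runs from about 10% at a correlation of 0.3, through 5% at 0.5, to no inflation at about 0.625, and the test is conservative above that.

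These figures rest on a mean of 6, an SD at its stated ceiling, 100 people, two complete timeframes and a two-sided test. They show a risk under the plan's own planning values and do not predict what the data will show. The case against the normality trigger depends less on the correlation: in every correlation simulated, the paired t test stayed between 2.4% and 2.7% on these skewed counts.

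**What to change.** In the H1 power paragraph, replace the Poisson sentence with an advance statement that any count model for UTIs will use a variance estimated from the data. Two forms would serve: a log-link Poisson GEE with person-clustered robust standard errors, or a mixed model with an over-dispersion parameter, such as negative binomial. Name one of them. The simulations above cover a robust standard error of the first kind (error 2.4% to 2.8% at every correlation tried). The negative binomial mixed model was not simulated. Remove the normality check as the trigger for choosing the model.

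Use the same wording in H3 for consistency, noting that the documents give no figures there from which inflation could be shown.

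The cost is a change of wording, with no new data or participants. Intervals would be about 15% wider than plain Poisson if the change variance is 16 (√(16/12) = 1.155), and about the same if it is 12.
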